10.3.3 Subgroup Analyses

The proportions and 95% confidence intervals for the primary outcomes (study objectives 1a and 1b) will be performed separately by age group (<55, 55-64, ≥ 65), sex, and race/ethnicity, cohort status determined at enrollment, and cohort status determined throughout the observations period (e.g., received an IRN during patch wear, received an ECG app-Inconclusive classification during patch wear). Chi-squared tests will be performed to determine if these proportions differ significantly by subgroup.

10.3.4 Additional Analyses

Subject accountability, baseline demographics and medical history, survey results, and adverse events will be summarized using descriptive statistics for the FAS. Baseline demographics and medical history will also be summarized for participants in the FOG. Additional details may be found in the SAP.

Additional analyses may be performed to gain further insight into the relationships between receiving notifications or app-based classifications and ePatch data. Importantly, we will additionally evaluate use of the IRN feature and behavioral response to notifications as captured in the 15 day PRO. Similarly, we will evaluate behavioral response to engaging a healthcare provider as captured in the 60 day PRO among those in the FAS by relevant participant characteristics.

Apple may perform additional analyses using participant data to support future product development.

10.4 Handling of Missing Data

This document contains information that is privileged or confidential and may not be disclosed unless such disclosure is required by applicable laws and regulations. The information in this document is the property of Apple Inc. and may not be reproduced, published, or disclosed to others without written authorization from Apple Inc.

Participants who do not respond to the 15 or 60 day PROs, do not have at least an hour of analyzable wear time from the ambulatory ECG monitor or do not return a patch within 45 days will be considered to have missing data. Methods for missing data such as multiple imputations will be implemented when performing analyses on the FAS or the EEAS. The assumptions of the missing data method will be evaluated in sensitivity analyses.

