7.4 Procedures for Ambulatory ECG Patch

7.4.1 BioTelemetry Flow

1. The Study Telehealth Provider will order the ECG patch from BioTelemetry and communicate information necessary for mailing ECG patch and study data management to BioTelemetry.
2. If the participant did not have Study Visit #1 within 30 days of enrollment, participant will still be able to receive a patch monitor and continue with study procedures including PROs, but they will not be included in the primary analyses.
3. BioTelemetry will mail the ambulatory ECG monitor to the participant.

This document contains information that is privileged or confidential and may not be disclosed unless such disclosure is required by applicable laws and regulations. The information in this document is the property of Apple Inc. and may not be reproduced, published, or disclosed to others without written authorization from Apple Inc.

4. The participant will wear the ambulatory ECG monitor for up to 7 days and mail the monitor back to BioTelemetry.
5. After the ambulatory ECG monitor has been worn by the participant for up to 7 days and returned back to BioTelemetry, BioTelemetry will perform data extraction and an initial technical read of the ambulatory ECG findings by trained ECG technicians. The ECG technician review will determine if the participant has any serious or potentially life-threatening abnormality. Although rare, this includes atrial fibrillation with sustained rapid ventricular rates, sustained ventricular tachycardia or ventricular fibrillation, high-degree heart block, and long pauses. If one of these urgent arrhythmias is identified, then the participant will be contacted and directed to local emergency care or advised how to seek local emergency care. Best attempt will be made to send the ECG report to participant's emergency care provider. After confirmation that a participant's ambulatory ECG data does not have any of these urgent arrhythmias, the ambulatory ECG study will be processed into the adjudication workflow. The adjudication workflow is described in a separate charter.
6. The adjudication process will result in generation of a final adjudicated report.
7. Once the adjudicated report is complete, it will be issued to the Study Telehealth Provider.

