7.4.2 Procedures for ECG patch wear

The BioTelemetry ePatch Monitor will be used for ambulatory ECG monitoring. The battery life with a single channel recording is 7 days. The participant will be instructed to wear the ePatch for up to 7 days. However, the data collected from a participant will be considered adequate for a participant with a minimum analyzable time of 1 hour.

BioTelemetry will send participants, via courier, an ambulatory ECG monitoring kit containing one sensor and two adhesive patches. If the adhesive patch is no longer functional, the sensor

This document contains information that is privileged or confidential and may not be disclosed unless such disclosure is required by applicable laws and regulations. The information in this document is the property of Apple Inc. and may not be reproduced, published, or disclosed to others without written authorization from Apple Inc.

can be moved to the backup adhesive patch. At the end of the recording period, the participant will be required to mail the monitor back to BioTelemetry using the supplied prepaid mailer.

In the event it is discovered that the participant never received the ePatch due to a shipping error or became lost in transit, then BioTelemetry will issue a second ePatch to that participant. Any subsequent loss of ePatches will not be replaced.

Approximately 14-20 days after enrollment it is expected that most participants will have completed wearing the patch for up to 7 days and will have returned the patch to BioTelemetry via a provided tracked USPS mailer. The ambulatory ECG monitor should be received by BioTelemetry within 45 days from enrollment. Those who return patches beyond 45 days after enrollment or do not begin wearing their patch within 14 days of patch shipment will be included in the fall-out subgroup, however they will still be eligible for a follow-up visit with the Study Telehealth Provider. Those who never return the ambulatory ECG monitor will also be placed in the fall-out subgroup.

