7.6 Procedures for Study Visit #2

Once the ePatch has been received by BioTelemetry and the final report has been adjudicated, BioTelemetry will issue a notification to the Study Telehealth Provider. The participant will be notified by way of a secure email that their patch report is ready and will be instructed to contact the Study Telehealth Provider for Study Visit #2 through a button in the app. It is expected that this visit will occur between 15-45 days after enrollment, depending on timing of ambulatory ECG monitor wear, mailing, and interpretation.

The Study Telehealth Provider will review the ambulatory ECG monitoring report with the participant and make any necessary recommendations to the participant. The Study Telehealth Provider will then refer participants with AF, any clinically relevant cardiac arrhythmias, or any non-urgent symptoms requiring follow up detected on patch monitoring to their primary health care provider for further treatment and diagnostic testing. For participants without established primary health care providers, the Study Telehealth Provider will offer referral per standard Study Telehealth Provider protocols. The ambulatory ECG monitoring report and visit summary will be made available to the participant and also to participant's physician or health care provider, if the participant provides the Study Telehealth Provider information of participant's physician and permission to send that physician a copy of the report. Any referral

This document contains information that is privileged or confidential and may not be disclosed unless such disclosure is required by applicable laws and regulations. The information in this document is the property of Apple Inc. and may not be reproduced, published, or disclosed to others without written authorization from Apple Inc.

visits will be conducted outside of the study, at the discretion of the participant, and at the cost of the participant.

Symptoms, disposition recommendations, and any adverse events reported will be logged.

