10.0 STATISTICAL CONSIDERATIONS

10.1 Analysis Sets

All analyses will be reported for the overall cohort, as well as by cohort status determined at enrollment: (1) Irregular Rhythm Notification, and status of (2) Afib or (3) Inconclusive via the ECG app (i.e., with at least 1 ECG recorded within the 14 days before study enrollment indicating classification of either AFib or Inconclusive, where the latter is defined as “Inconclusive,” “Heart Rate Over 120,” or “Heart Rate Under 50”).

The Full Analysis Set (FAS) will consist of all enrolled participants who complete the informed consent process. This analysis set will be used to summarize subject demographics, medical history, adverse events, self-reported health status, diagnosis, and contact with the health care provider.

The ePatch eligible analysis set (EEAS) will consist of those in the FAS deemed eligible to receive an ePatch at Study Visit #1.

The ePatch Analysis Set (EAS) will consist of all those in the EEAS who receive and return an ePatch with at least 1 hour of usable data and who do not belong to the Fallout Group.

The Fallout Subgroup Analysis Set (FOG) will consist of participants meeting the criteria of Section 7.10. Demographic and medical history information will be presented for this analysis set.

Objectives 1a, 1b, and 2b and 2c will be conducted using the EAS, whereas Objective 2a will be conducted using the EEAS. The analyses for Objectives 1a, 1b, and 2b and 2c will be repeated in the EEAS as a sensitivity analysis using appropriate methods for handling missing data.

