3. ANALYSIS SETS

The Full Analysis Set (FAS) will consist of all enrolled participants who complete the informed consent process. This analysis set will be used to summarize subject demographics, medical history, adverse events, self-reported health status, diagnosis, and contact with the health care provider.

The ePatch Eligibility Analysis Set (EEAS) will consist of those in the FAS deemed eligible to receive an ePatch at Study Visit #1. This analysis set will be used to assess Objective 2a.

The ePatch Analysis Set (EAS) will consist of all those in the EEAS who receive and return an ePatch with at least 1 hour of usable data and who do not belong to the Fallout Subgroup. This analysis set will be used to assess Objectives 1a, 1b, and 2b and 2c. We will repeat these analyses in the EEAS as a sensitivity analysis using appropriate methods for handling missing data.

The Fallout Subgroup Analysis Set (FOG) will consist of participants who enroll and complete the informed consent process but otherwise do not complete the study. Reasons for study incompleteness include; failure to contact Study Telehealth Provider within 30 days of enrollment, being deemed ineligible at Study Visit #1 for ePatch wear due to emergent symptoms, ePatch not returned within 45 days of enrollment, failure to start wearing ePatch within 14 days of shipment, unable to verify at Study Visit #1 a study eligible IRN or ECG-app notification, study withdrawal (i.e., withdrawal of consent), or lost to follow-up (i.e., death). We will present demographic and medical history information for this analysis set.

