Additional analyses may be performed to gain further insight into the relationships between receiving notifications or app-based classifications and ePatch data. Importantly, we will additionally evaluate use of the IRN and ECG app features and behavioral response to notifications as captured in the 15 day PRO. Similarly, we will evaluate behavioral response to engaging a healthcare provider as captured in the 60 day PRO by relevant participant characteristics.

To understand the sensitivity of our findings for study objectives utilizing the EAS that requires at least 1 hour of useable data from participants in the EEAS, we will vary the requirement that participants with less than 1 hour of wear time be considered as missing their ECG data. We will also conduct additional sensitivity analyses considering the following alternative minimum wear times: 6 hours, 1 day, 2 days, and 5 days.

Adverse Events

A participant will be counted once for a reported AE even if the participant had multiple occurrences of that AE. We will summarize the proportion of participants reporting anxiety and rash in the EEAS and EAS. All AEs will be collected; however, these AEs are of most interest to the study device (anxiety) and are highest risk in the study (rash).

Adverse Events	N EEAS	% EEAS	N EAS	% EAS
Anxiety				
Rash				

The participant incidence of all serious adverse events will be presented for each analysis set by age group and overall.

Age group, yrs	N SAEs	N unique participants with SAEs	SAEs/participants with SAEs
< 55			
55-64			
65+			
Overall			

Analysis of Fall-Out Subgroup

The FOG (a subset of the FAS) will include participants who are enrolled but otherwise do not complete the study. Possible reasons are listed in Section 3. We will describe baseline characteristics for this group and for those in the FOG that have completed the PRO, we will report rates of contact with a non-study healthcare provider.

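### Patches returned after day 45 count as missing even when they hold usable data, so the EEAS sensitivity analysis would impute AF results that were observed

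*Combined protocol and SAP*

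**What the plan says.** Protocol 10.4 and SAP 4.6 carry the same missing-data rule. A participant has missing data for any of three reasons: no reply to a PRO survey, less than an hour of analyzable patch recording, or late return. On the last, participants who "do not return a patch within 45 days will be considered to have missing data". The conditions are joined by *or*, so late return is enough on its own. Missing data in the FAS and EEAS are then handled by methods of which multiple imputation is the named example, with a promise to examine the assumptions.

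The EEAS "will consist of those in the FAS deemed eligible to receive an ePatch at Study Visit #1" (SAP 3; protocol 10.1 agrees). Return date plays no part in that definition. The primary set, the EAS, requires an hour of usable data and also excludes everyone in the Fallout group. Under protocol 10.1 the analyses for Objectives 1a, 1b, 2b and 2c "will be repeated in the EEAS as a sensitivity analysis using appropriate methods for handling missing data".

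On late patches, protocol 7.4.2 says: "Those who return patches beyond 45 days after enrollment or do not begin wearing their patch within 14 days of patch shipment" go to the fall-out subgroup, "however they will still be eligible for a follow-up visit with the Study Telehealth Provider". Protocol 7.4.1 describes what happens to a returned monitor: "BioTelemetry will perform data extraction and an initial technical read of the ambulatory ECG findings by trained ECG technicians", then adjudication, with no cut-off by return date. Protocol 7.6 places Visit #2 after that step: "Once the ePatch has been received by BioTelemetry and the final report has been adjudicated", the provider is notified and the participant is invited to the visit.

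**The concern.** The EEAS analysis is the plan's check on whether restricting the primary analysis to on-time, usable patches distorts the AF proportions. It is most useful where it brings in real results that the EAS leaves out, and late patches are the obvious source. The rule sets those results aside and puts model predictions in their place, so the check leans on an assumption where data exist.

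Late returners may differ from on-time returners in either direction. SAP 4.7 itself allows that people who do not return a patch may be less sick, so return behaviour is acknowledged as possibly related to AF. Observed late results are also direct evidence on the assumptions that protocol 10.4 and SAP 4.6 promise to examine.

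**Working it through.** **1. Where a late patch with at least 1 hour of usable data ends up**

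| Analysis | Rule | Use of the late AF result |
|---|---|---|
| EAS, primary (protocol 10.1, SAP 3) | Usable data and not in Fallout | Excluded by design |
| EEAS repeat (protocol 10.1 and 10.4, SAP 3 and 4.6) | Eligible at Visit #1; missing if under 1 hour or late | Participant kept, result treated as missing |
| Wear-time sensitivity analyses (SAP 4.3) | Minimum wear set to 6 hours, 1, 2 or 5 days | Return limit not varied, so not used |
| Fall-out analysis (SAP 4.3) | Baseline data and PRO contact | Not used |
| General commitments (protocol 10.3.4 and 10.4, SAP 4.3 and 4.6) | Check assumptions; further analyses possible | Late patches not named |

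For the fall-out row the SAP's words are: "We will describe baseline characteristics for this group and for those in the FOG that have completed the PRO", followed by the rate of contact with a non-study provider. No AF proportion is planned there.

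**2. Does the late result exist?** Protocol 7.4.1 reads and adjudicates returned monitors without a date limit. Protocol 7.4.2 keeps late returners eligible for the follow-up visit, and protocol 7.6 puts that visit after adjudication. Together these imply that a late patch is read and adjudicated. Two other places in the SAP point the same way. The concordance definition in SAP 4.5 asks for 1 hour of usable data and sets no return limit. The missing-data bias paragraph in SAP 4.7 concerns people with no analyzable recording, which does not describe a late usable patch.

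**3. Is day 45 a recording window?** Inputs: Visit #1 by day 30 (protocol 7.4.1), wear begun within 14 days of shipment and worn for up to 7 days (protocol 7.4.2). Assuming shipment on the day of the visit:

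30 + 14 + 7 = day 51, before return mailing.

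A participant can meet every other deadline and still be late. Conversely, a patch worn on days 10 to 17 and mailed on day 50 was recorded as close to the notification as many on-time patches, yet it is missing. Day 45 limits return, not recording.

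**4. Size.** The plan has no figure to reproduce: it gives no late-return rate, and the 35% attrition allowance is not split by cause. Protocol 7.4.2 expects most patches back at about day 14 to 20, so late patches may be few. Holding all other imputed values fixed,

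shift in EEAS estimate = s × (p_observed − p_imputed),

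where s is the share of the EEAS that is late with usable data, and the bracket is the gap in AF proportion among those participants. Both are assumed here.

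| s | gap 10 points | gap 20 points | gap 30 points |
|---|---|---|---|
| 2% | 0.2 | 0.4 | 0.6 |
| 5% | 0.5 | 1.0 | 1.5 |
| 10% | 1.0 | 2.0 | 3.0 |

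Entries are percentage points and take either sign. With no gap the shift is zero.

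**5. The end of the 45 days.** The start is enrollment in protocol 7.4.2 and 7.12 and in SAP 1.2 and SAP 3; only protocol 10.4 and SAP 4.6 shorten the phrase. The end event varies: receipt by the patch vendor in one sentence of protocol 7.4.2, mailing by the participant in SAP 1.2, and an undefined return in protocol 7.12 and 10.4 and in SAP 3 and 4.6. A patch mailed on day 43 and received on day 47 is in the EAS under mailing and in Fallout under receipt.

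**The case against.** The best defence is that treating out-of-window measurements as missing is a common convention. SAP 4.7 already warns that the patch follows the notification and may miss the triggering episode, and a late patch may lie further away still. That stands as a reason to keep the on-time EAS primary and to label late results. It does not justify imputing them, because the limit acts on return rather than on recording.

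A second defence is that the plan leaves room: multiple imputation is only an example, the assumptions will be checked, and additional analyses are allowed. This is true, but any missing-data method starts from the classification that makes these results missing, and none of the general commitments mentions late patches.

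On the end event, protocol 7.4.2 puts receipt and return in adjacent sentences, so receipt is a natural reading, and the tracked mailer should make the dates recoverable. That reduces the matter to a clarification.

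Three stronger readings are tempting and not supported:

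- *The starting date of the 45 days is not fixed.* It is fixed at enrollment in four sections; only the end event is unclear.
- *The rule is uneven, because a late Visit #1 or late wear start also leads to Fallout but counts as observed in the EEAS.* This is at most an inference from those cases not being listed in protocol 10.4 and SAP 4.6. Protocol 4.1, 7.4.1 and 7.12 say that such participants are or may be left out of some analyses, and do not settle the EEAS.
- *The shift can be judged against the planned interval width of 0.10.* That width is for 400 returned patches per group, the EAS target. An EEAS interval has a different sample size and carries imputation variance.

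**Conclusion.** The concern holds for the EEAS sensitivity analysis. As written, AF results from late but usable patches are declared missing and become subject to imputation, and no specified analysis recovers them. This rests on the plain wording of protocol 10.4 and SAP 4.6, and on the implication that late patches are read and adjudicated.

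The consequence is modest. The study is descriptive, and this limb leaves the primary EAS estimates unchanged. Across the assumed range the shift is 0.2 to 3.0 points in either direction; the true size cannot be known without the number of late usable patches, and it may be close to zero. This is an inexpensive improvement rather than a threat to the main conclusions. The mailed-or-received wording is a minor point, but it does reach the primary analysis, because it decides EAS membership for patches in transit around day 45.

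**What to change.** 1. In protocol 10.4 and SAP 4.6, state that for the EEAS analysis of Objectives 1a, 1b, 2b and 2c the ECG outcome is missing only when no patch with at least 1 hour of usable data exists. At minimum, keep the present rule and add a supplementary EEAS analysis that uses late usable patches.
2. Report the number of late usable patches by cohort (IRN, ECG app-AFib, ECG app-inconclusive).
3. Keep the on-time EAS as the primary set.
4. Define the end of the 45 days once, as mailing or as receipt, and use that definition in protocol 7.4.2, 7.12 and 10.4 and in SAP 1.2, 3 and 4.6, repeating that the count starts at enrollment.

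The cost is wording in both documents and one count per cohort, or one extra analysis under the minimum option, with no new data collection. The drawback is that some late patches may have been recorded further from the notification; the report should say so beside the EEAS result.

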10.5 Sample Size and Power Considerations

This clinical study is not designed to test any pre-specified statistical hypotheses. Because all participants enrolling in this clinical trial will either have received an irregular rhythm notification (IRN) or an ECG app-AFib classification, this sample size justification applies to Objectives 1a and 1b. To address our aims, we require 400 IRN participants that are exclusively in the IRN group (i.e., who do not enter the study via the ECG app), who are deemed eligible for ePatch receipt and who return their ePatches, and 400 participants who exclusively enroll via the ECG-app classification of AFib, who are deemed eligible for ePatch receipt and who return their ePatches. This sample size provides sufficient precision for our purposes, yielding a 95% confidence interval with a width that is no greater than 0.10 when addressing the primary objectives. Further, it does not require assessment or unblinding of ePatch results on an ongoing basis. If, after enrolling 500 participants, we observe that there is 50% overlap or greater between participants who enroll through both the IRN and the ECG app, we will modify our targeted enrollment with the understanding that the reporting of findings will be accompanied with a detailed context of the types of subjects that contribute to both the point estimates of interest. Given these considerations, a targeted enrollment of 2600 participants is suggested. This allows for approximately a 35% attrition rate and a 50% overlap between participant types (IRN vs ECG-app).

